## VII. Assessment of Fever

Days	Temperature (morning)	
	Present	Absent
Day 1		
Day 7		
Day 14		

## VIII. Assessment of Convulsion

Days	Convulsion	
	Present	Absent
Day 1		
Day 7		
Day 14		

IX. Assessment of Abnormal mental status

Days	Abnormal mental status	
	Present	Absent
Day 1		
Day 7		
Day 14		

X. Laboratory (hematological and biochemical) parameters

hematological and biochemical parameters	Baseline	Day-7	Day-14
HGB (g/dL)			
NEUT ( $10^3/\mu\text{L}$ )			
PLT ( $10^3/\mu\text{L}$ )			
ALT (U/L)			
AST (U/L)			
Serum creatinine ( $\mu\text{mol/L}$ )			
Potassium (mmol/L)			

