#### **3.2. Objectives**

1. To find out the back-ground characteristics of patients with HIV-associated cryptococcal meningitis
2. To describe the clinical effectiveness of amphotericin B with flucytosine-fluconazole combination therapy by assessing clinical parameters at day 1, day 7 and day 14
3. To determine the severity of headache before and after treatment by numerical rating scale
4. To describe the clinical safety of amphotericin B with flucytosine-fluconazole combination therapy by assessing hematological and biochemical parameters by DAIDS grading at baseline, day 7 and day 14

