#### **4.8. Materials and Methods**

After getting approval from medical superintendent, patients with HIV-associated cryptococcal meningitis admitted to inpatient departments of SHW, SHM and SHT will be studied. They will be given IV infusion of amphotericin B (1 mg/kg/day) and oral flucytosine (100 mg/kg) for one week followed by oral fluconazole (1200 mg/day) for one week according to the hospital standard treatment guideline chosen by the physician depends on patient's clinical condition. Before giving treatment, informed consent will be obtained.

All patients meeting the inclusion criteria will be studied under the supervision of experienced physicians. Baseline data for assessing clinical effectiveness such as fever, convulsion and abnormal mental status and for safety such as hematological and biochemical parameters (hemoglobin, neutrophil, platelet, ALT, AST, serum creatinine and serum potassium level) will be noted from medical charts. Hematological and biochemical parameters will be graded according to DAIDS grading. Assessment of headache and its severity will be done by numerical rating scale under the supervision of physician.

Seven days and fourteen days after treatment, clinical effectiveness parameters such as headache, fever, convulsion, abnormal mental status and death will be reassessed. Clinical safety concerning hematological and biochemical parameters like hemoglobin, neutrophil, platelet, ALT, AST, serum creatinine and serum potassium level will also be reassessed and graded according to DAIDS grading by reviewing from patient's medical charts at seven and fourteen days. With regard to severity of headache, it will be documented by using numerical rating scale at weekly intervals for two weeks. Clinical effectiveness parameters (headache, fever, convulsion, abnormal mental status and death) and hematological and biochemical parameters will be described. The results will be documented for data analysis.

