###### **(ii) Fever**

It is defined as rise in body temperature above 37 °C (98.6 °F) in the morning.

(iii) Convulsion

It is defined as a medical condition where body muscles contract and relax rapidly and repeatedly, resulting in uncontrolled actions of the body.

(iv) Abnormal mental status

It is defined as patients is somnolent, lethargy, disoriented and disruptions in perception and behavior.

(4) Clinical safety

Clinical safety will be assessed by laboratory defined adverse events. Adverse event is defined as any untoward medical occurrence in a subject to whom a medicinal product has been administered including occurrences which are not necessarily caused by or related to that product (Division of AIDS, 2017). Laboratory parameters (hematological and biochemical parameters) such as HGB, NEUT, PLT, ALT, AST, serum creatinine, serum potassium level will be graded according to DAIDS grading in appendix 3. Bone marrow suppression is defined as Grade 3 and 4 adverse events in one or more of anaemia, neutropenia and thrombocytopenia.

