#### 4.12. Algorithm

## 5. DUMMY TABLES

Table 4. Number of Cryptococcal meningitis in patients with HIV infection enrolled from individual specialist hospital

Hospital	Number (N)	Percentage (%)
Specialist hospital Waibargi		
Specialist hospital Mingalardon		
Specialist hospital Thakeyta		
Total		

Table 5. Distribution of age among study group of Cryptococcal meningitis in patients with HIV infection

Age (completed years)	Amphotericin B, Flucytosine plus Fluconazole group	
	Number	Percentage
≤20		
21-40		
>40		
Total		

Table 6. Distribution of gender among study group of Cryptococcal meningitis in patients with HIV infection

Gender	Amphotericin B, Flucytosine plus Fluconazole group	
	Number	Percentage
Male		
Female		
Total		

Table 7. Frequency distribution of headache among study group by Numerical rating Scale at day-1, day-7 and day-14

Days	Headache	Amphotericin B, Flucytosine plus Fluconazole group	
		Number	Percentage
day-1	No pain		
	Mild		
	Moderate		
	Severe		
	Intolerable		
Day-7	No pain		
	Mild		
	Moderate		
	Severe		
	Intolerable		
Day-14	No pain		
	Mild		
	Moderate		
	Severe		
	Intolerable		

Table 8. Clinical effectiveness of study group by assessing presence of headache, fever, convulsion, abnormal mental status and death at day-1, day-7 and day-14

Clinical parameters	Amphotericin B, Flucytosine plus Fluconazole group					
	Day 1		Day 7		Day 14	
	N	%	N	%	N	%
Headache						
Fever						
Convulsion						
Abnormal mental status						
Death						

Table 9. Laboratory-defined adverse events of amphotericin B, flucytosine and fluconazole at baseline and day-7 and day-14 by DAIDS grading

Days	DAIDS Grading	Hematological parameters & Biochemical parameters								Total
		Anaemia N (%)	Neutropenia N (%)	Thrombocytopenia N (%)	Elevated ALT level N (%)	Elevated AST level N (%)	Hypokalemia N (%)	Hyper creatinemia N (%)		
Baseline	Grade 1									
	Grade 2									
	Grade 3									
	Grade 4									
Day-7	Grade 1									
	Grade 2									
	Grade 3									
	Grade 4									
Day-14	Grade 1									
	Grade 2									
	Grade 3									
	Grade 4									

Table 10. Proportion of patients with grade 3 and 4 adverse events of hematological parameters at baseline, day-7 and day-14

	Grade 3 and 4 adverse events	Baseline		Day -7		Day -14	

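### Convulsion, an episodic event, is recorded only as present or absent at days 1, 7 and 14 with no look-back window, so on the natural reading on-treatment convulsions are understated

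*Combined protocol and SAP*

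**What the plan says.** Convulsion is one of five clinical effectiveness parameters (section 4.10, item 3). Objective 2 in section 3.2 describes effectiveness "by assessing clinical parameters at day 1, day 7 and day 14". Section 4.8 gives the follow-up schedule: "Seven days and fourteen days after treatment, clinical effectiveness parameters such as headache, fever, convulsion, abnormal mental status and death will be reassessed". For baseline it refers to "Baseline data for assessing clinical effectiveness such as fever, convulsion and abnormal mental status", taken from medical charts, without saying how far back the chart is read.

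In Annex 1, the part headed "VIII. Assessment of Convulsion" is a grid of three rows (day 1, day 7, day 14) and two columns (present, absent). It has no field for a date, a count or an interval. Dummy Table 8 carries the grid into the results under the title "Clinical effectiveness of study group by assessing presence of headache, fever, convulsion, abnormal mental status and death at day-1, day-7 and day-14", with a number and a percentage for each day and no cumulative row.

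The operational definition in section 4.10 describes the event itself: "It is defined as a medical condition where body muscles contract and relax rapidly and repeatedly". It does not say whether a tick refers to that day, the past 24 hours or the time since the last assessment.

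Seizures have no other route into the data. On safety, section 4.10 states: "Clinical safety will be assessed by laboratory defined adverse events". Section 4.11 promises close monitoring and reporting of adverse reactions to the physician, but no form field or table receives that information.

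**The concern.** Headache, fever and altered mental status can persist for days, so a look on a fixed day is a reasonable sample of them. A convulsion is over in minutes. A patient who convulses on days 3 and 5 but not on day 7 can properly be ticked absent at day 7. A patient who convulses on day 4 and dies on day 6 has no follow-up row in which the convulsion could appear.

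The percentage of patients who convulse during two weeks of treatment is therefore at stake. Table 8 presents the convulsion row as clinical effectiveness, and without a comparator group nothing else in the results would show that a low figure came from the recording method.

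**Working it through.** **The plan's own figure.** The only computed design figure is the sample size in section 4.7.1, n = z²p(1−p)/d²:
- Safety: 1.96² × 0.83 × 0.17 / 0.14² = 27.66.
- Effectiveness (headache improvement): 1.96² × 0.8 × 0.2 / 0.15² = 27.32.

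The stated 27 is reproduced by truncation; rounding up gives 28. Neither calculation involves convulsion, so 27 serves below only as a denominator.

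**Which reading of the tick is natural.** The fever grid has the same layout and records a morning temperature on the listed day. Headache is scored on the same listed days. Objective 2 and Table 8 both speak of assessment at those days. The on-the-day reading is therefore the natural one, although no sentence states it.

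**Days observed on that reading.** Days 2-14 are 13 days, of which days 7 and 14 are observed: 2/13 = 15%. The other 11/13 = 85% are not.

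**Chance that an affected patient is never flagged after day 1.** Assume k seizure-days placed evenly at random among the 13 days. The chance that none falls on day 7 or day 14 is C(11,k)/C(13,k):

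| k seizure-days in days 2-14 | Calculation | Never flagged |
|---|---|---|
| 1 | 11/13 | 85% |
| 2 | 55/78 | 71% |
| 3 | 165/286 | 58% |
| 5 | 462/1287 | 36% |
| 7 | 330/1716 | 19% |

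**Early clustering.** If the daily chance of a seizure halves every 2, 3 or 5 days (an assumption), weight day t by 0.5^((t−1)/h), where h is the half-life. Days 7 and 14 then hold 6%, 8% or 11% of the days 2-14 weight, against 15% under an even spread.

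**In patients, as an illustration.** The documents give no on-treatment seizure rate. Section 2.1.5 cites presenting rates of 19.2% (African trial) and 41.3% (an earlier Myanmar study). They are borrowed here only to show scale; 10% is added as a lower value.

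| Assumed true share convulsing in days 2-14 | Patients of 27 | Flagged, 1 seizure-day each (× 2/13) | Flagged, 3 seizure-days each (× 121/286) |
|---|---|---|---|
| 10% | 2.7 | 0.4 | 1.1 |
| 19.2% | 5.2 | 0.8 | 2.2 |
| 41.3% | 11.2 | 1.7 | 4.7 |

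**Trend from day 1.** Two cases follow from the undefined baseline window.
- Suppose day 1 records presenting history and the later ticks cover one day each. If 19.2% convulsed before treatment, and 19.2% convulse in days 2-14 on one day each, the expected figure at a single follow-up visit is 0.192 × 1/13 = 1.5%. The row drops from 19.2% to 1.5% with no treatment effect.
- Suppose all three ticks cover the same length of time. A constant seizure rate then gives constant percentages, and the trend need not be biased.

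**The alternative reading.** If the day-7 and day-14 ticks mean 'since the last assessment', every day is covered and nothing is missed by design.

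**The case against.** The strongest reply is that the one-day window is inferred. Section 4.8 and Table 8 list death beside convulsion at days 7 and 14, and death is naturally read as having occurred by that visit, so these columns need not all be one-day snapshots. This stands: a reader might infer that the plan certainly misses most seizures, and the documents do not support that as fact. It does not rescue the form, however. With no window stated, staff at three hospitals may complete the field differently, and the pooled percentage then has no clear meaning.

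Second, the size depends on how often affected patients convulse. With 5 or 7 seizure-days, most patients are flagged. This also stands, and it is why the figures are given by number of seizure-days.

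Third, a reader might infer that the recording makes the regimen look more effective than it is. That requires day 1 to cover a longer period than the later ticks. Charts at admission may well include the presenting history, but the documents fix no baseline window, and the form gives all three rows the same label.

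Fourth, this is a single-group descriptive study with no test and no success threshold, and convulsion does not drive the sample size. That limits the consequence to one row of Table 8.

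**Conclusion.** The point holds as a recording weakness that is cheap to correct. Followed on its natural reading, the plan samples a brief event on 2 of 13 post-baseline days and understates how many patients convulse on treatment. The 85%, 71% and 58% chances of never being flagged rest on that reading, on 1, 2 or 3 seizure-days per affected patient, and on an even spread over days 2-14. Clustering in the first days would leave a smaller share of seizure-days observed; a since-last-assessment reading would remove the loss altogether.

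Two conclusions go further than the documents allow: that most seizures are certainly lost, and that the day-1 to day-14 change certainly favours the regimen. What can be said is that cumulative occurrence is understated on the natural reading, and that the trend cannot be interpreted until the baseline window is stated.

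**What to change.** In part VIII of the pro forma, replace the day-7 and day-14 ticks with 'any convulsion, days 2-7' and 'any convulsion, days 8-14', with dates taken from the inpatient chart. Add the same intervals to the definition in section 4.10. In Table 8, label the convulsion row 'any in period' and report days 2-7, days 8-14 and a cumulative days 2-14 figure.

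Handle baseline explicitly. Either give it a stated window of similar length, for example the 7 days up to day 1, or label it as presenting history and do not read the change from it as effectiveness. An open-ended baseline set against week-long follow-up periods would keep the windows unequal.

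The cost is new wording in the form, the definition and one table, plus a few more chart days to read per patient. The patients are inpatients, and their charts are already the source of the baseline clinical data and the laboratory values. The change should be made before data collection starts so that all three hospitals apply it alike.

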### Annex 3. Scale

#### Headache severity assessment

A numeric rating scale (NRS) is used to assess the severity of headache. The NRS score range from zero to 10. Headache severity will be categorized according to the number given by patients for their headache. Headache will be categorized as no pain, mild, moderate, severe, and intolerable when scores are 0, 1-3, 4-6, 7-9, and 10. Headache will be evaluated by administration of a headache questionnaire at the time of admission and during the follow up.

ခေါင်းကိုက်ရာတွင်နာကျင်မှုအဆင့်နှင့်သတ်မှတ်ချက် မှတ်တမ်း

သင်၏နာကျင်မှုအဆင့်ကို သိသာစေရန် အသင့်တော်ဆုံး နံပါတ်တစ်ခုကိုရွေးချယ်ပေးပါ။

0      1      2      3      4      5      6      7      8      9      10

လုံးဝ

အလွန်အမင်း

မနာကျင်ပါ

နာကျင်မှုရှိပါသည်

**Division of AIDS (DAIDS) Table for Grading the Severity of Adult and Pediatric Adverse Events**

Parameter	Grade 1 Mild	Grade 2 Moderate	Grade 3 Severe	Grade 4 Potentially life- threatening
Hemoglobin, Low (g/dL) $\geq$ 13 years of age (male only)	10.0 - 10.9	9.0 - 10.0	7.0 - 9.0	< 7.0
$\geq$ 13 years of age (female only)	9.5 - 10.4	8.5 - 9.5	6.5 -8.5	< 6.5
Absolute Neutrophil Count (ANC), Low (cells/L)	0.800-1.000 x $10^9$	0.600-0.799 $x 10^9$	0.400-0.599 $x 10^9$	< 0.400 x $10^9$
Platelets, Decreased (cells/L)	100-125 x $10^9$	50-100 x $10^9$	25- 50 x $10^9$	< 25 x $10^9$
ALT or SGPT, High Report only one	1.25-2.5 ULN	2.5-5.0x ULN	5.0 - 10.0 x ULN	$\geq$ 10.0 x ULN
AST or SGOT, High Report only one	1.25-2.5 x ULN	2.5 - 5.0 x ULN	5.0 -10.0 x ULN	$\geq$ 10.0 x ULN
Creatinine, High	1.1-1.3 x ULN	> 1.3 -1.8 x ULN OR Increase to 1.3 - 1.5 x participant's baseline	> 1.8 - 3.5 x ULN OR Increase to 1.5 to < 2.0 x participant's baseline	$\geq$ 3.5 x ULN OR Increase of $\geq$ 2.0 x participant's baseline
Potassium, Low (mEq/L; mmol/L)	3.0 -3.4	2.5 - 3.0	2.0- 2.5	< 2.0
	3.0 -3.4	2.5- 3.0	2.0 -2.5	< 2.0

**Normal range of laboratory (hematological and biochemical) parameters in  
SHW, SHM and SHT**

Hematological and biochemical parameters	Normal Range
HGB (g/dL)	11-16
NEUT ( $10^3/\mu\text{L}$ )	2-7.5
PLT ( $10^3/\mu\text{L}$ )	150-400
ALT (U/L)	10-60
AST (U/L)	10-50
Serum creatinine ( $\mu\text{mol/L}$ )	53.0-114.9
Potassium (mmol/L)	3.5-5.5

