Even where flucytosine (5FC) is available, it is often not administered because of overstated fears regarding toxicity (Loyse et al., 2013). The most serious drug-related adverse effect of 5FC is bone marrow suppression and hepatotoxicity (Vermes et al., 2000). In California's study, 5FC had been discontinued in over half of the patients because of cytopenia (Chuck & Sande, 1989). One patient in South Africa study also was discontinued 5FC because of thrombocytopenia on day-4 and the regimen was switched early to fluconazole (Bicanic et al., 2008). And also grade-4 neutropenia was recorded in 3.2% of the patients with 5FC (Molloy et al., 2018). But

in Thailand study, the treatment was well tolerated and there was no severe bone-marrow depression with 5FC (Brouwer et al., 2004).

Regarding amphotericin B Deoxycholate, its major drug-related adverse effects include nephrotoxicity and anemia (Bicanic et al., 2015). In Vietnam trial, Grade 3 and 4 anaemia were most prominent between amphotericin B plus flucytosine (35%) and amphotericin B plus fluconazole group (29%) (Day et al., 2013). Renal impairment occurs in nearly all patients treated with clinically significant doses of amphotericin. Fluconazole is relatively nontoxic, but reported to cause abnormalities in liver enzymes and very rarely, clinical hepatitis (Lampiris & Maddox, 2018).

Although WHO treatment guidelines recommend treatment regimen containing flucytosine as the preferred therapy, in clinical practice, treatment is highly variable due to drug costs, availability, and ability to monitor and manage drug-related toxicities (Perfect, 2010). A previous study was carried out in Mandalay for cryptococcal meningitis with fluconazole monotherapy by Than-Maung in 2006 and amphotericin B monotherapy by Myo-Thet-Naing in 2013 but the effectiveness and safety of amphotericin with flucytosine and fluconazole combination regime have not been studied in Myanmar. Thus, this study will provide information regarding the clinical effectiveness and safety of this treatment regimen for management of HIV-associated cryptococcal meningitis in Myanmar.

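### Table 9 grades creatinine by level alone at baseline but by level or rise at days 7 and 14, so the rows are not like for like

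*Combined protocol and SAP*

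**What the plan says.** Objective 4 (section 3.2) describes safety "by assessing hematological and biochemical parameters by DAIDS grading at baseline, day 7 and day 14". Dummy Table 9 (section 5) carries this out "at baseline and day-7 and day-14 by DAIDS grading", with one creatinine column headed "Hyper creatinemia N" (%) and rows for grades 1 to 4 at each visit.

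The grading rule is in the DAIDS table in Annex 3. Grade 1 creatinine is defined by ULN only. Grades 2 to 4 each have a ULN criterion and an alternative relative to the participant's baseline:

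- Grade 2: "Increase to 1.3 - 1.5 x participant's baseline" is the alternative.
- Grade 3: "> 1.8 - 3.5 x ULN OR Increase to 1.5 to < 2.0 x" the participant's baseline.
- Grade 4: the alternative is a rise of at least "2.0 x participant's baseline".

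Creatinine is the only one of the seven Table 9 parameters with a baseline-relative criterion. Annex 3 gives the sites' normal range as 53.0 to 114.9 µmol/L. Sections 4.8 and 4.10 refer only to DAIDS grading, and section 4.9 plans numbers and percentages. No section says which creatinine criterion applies at which visit, or that the two will be shown separately.

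**The concern.** The study has a single treatment group, so the baseline row of Table 9 is the only internal reference for the later rows. For creatinine, that row can record only a high level, while the day 7 and day 14 rows can record a high level or a rise. A reader who sets the grade 3/4 percentages side by side will take the difference as a change on one scale, which it is not.

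The combined column also cannot separate a patient whose creatinine is well above the normal limit from one whose creatinine rose by half but stayed within range. Table 9 is the only planned table that reports renal function, and section 1.1 expects a renal effect: "Renal impairment occurs in nearly all patients treated with clinically significant doses of amphotericin".

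**Working it through.** The plan gives no computed creatinine figure, so there is none to reproduce.

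**Inputs (Annex 3).** Lower limit 53.0 and ULN 114.9 µmol/L. ULN multiples: 1.1, 1.3, 1.8 and 3.5. Baseline multiples: 1.3, 1.5 and 2.0. I take the participant's baseline to be the baseline value on the pro forma, and the combined grade to be the higher of the two.

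**1. Baseline row.** Baseline ÷ baseline = 1.0, below the lowest ratio threshold of 1.3. Only the ULN criterion can assign a grade:

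| Grade | ULN cut-off (µmol/L) |
|---|---|
| 1 | from 1.1 × 114.9 = 126.4 |
| 2 | above 1.3 × 114.9 = 149.4 |
| 3 | above 1.8 × 114.9 = 206.8 |
| 4 | from 3.5 × 114.9 = 402.2 |

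**2. Which criterion gives grade 3 first after treatment.** The ratio criterion comes first when 1.5 × baseline < 206.8, that is, when baseline < 206.8 ÷ 1.5 = 137.9 µmol/L. This covers the whole normal range.

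**3. When a graded value can still lie within the normal range.** The condition is multiple × baseline ≤ 114.9.

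| Grade | Highest baseline (µmol/L) | Share of the width of the normal range (61.9) |
|---|---|---|
| 2 | 114.9 ÷ 1.3 = 88.4 | (88.4 − 53.0) ÷ 61.9 = 57% |
| 3 | 114.9 ÷ 1.5 = 76.6 | (76.6 − 53.0) ÷ 61.9 = 38% |
| 4 | 114.9 ÷ 2.0 = 57.45 | (57.45 − 53.0) ÷ 61.9 = 7% |

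These are shares of the interval, not of patients.

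**4. Examples.**

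- 60 to 90 µmol/L: 90 ÷ 60 = 1.5 and 90 ÷ 114.9 = 0.78 × ULN. This is grade 3 by ratio and ungraded by ULN. The printed grade 2 band also ends at 1.5, so the higher grade is taken here. A rise from 60 to 95 (1.58 × baseline, 0.83 × ULN) avoids the tie and gives the same result.
- 106 µmol/L: ungraded as a baseline value (0.92 × ULN), but grade 4 by ratio at day 7 if the baseline was 53.

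**5. The wording of grade 4.** Grades 2 and 3 speak of an increase *to* a multiple, grade 4 of an increase *of* one. If grade 4 means a rise by 2.0 × baseline, the value must reach 3 × baseline, and a within-range grade 4 needs a baseline of at most 114.9 ÷ 3 = 38.3, below the lower limit of 53.0. Values from 2 to just under 3 × baseline would then have no ratio grade, so *to* is the more coherent reading. The grade 3 result holds either way.

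**6. Direction.** The combined grade is never lower than the ULN grade, so any departure from ULN-only grading at days 7 and 14 is upwards.

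**The case against.** **The scale is a standard one, and grading a rise is its purpose.** This stands. The table for managing amphotericin B toxicity in section 2.1.11 also treats a creatinine rise of at least twofold from baseline as elevated creatinine, without reference to ULN. A reader might infer that the plan mislabels normal creatinine as toxicity. The documents do not support that, because a ratio grade marks a real change.

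**The rule creates no increase by itself.** This stands too. A patient with stable creatinine has the same grade at all three visits, and the ratio criterion needs a rise to at least 1.3 × baseline. Section 4.10 ties adverse events to a product having been given, so a change criterion has nothing to detect before treatment. It would be wrong to call the rise from baseline to day 7 an artefact.

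**The ratio criterion may affect few patients.** It is tempting to read section 1.1 as showing that this criterion will dominate the column. The documents give no creatinine distribution. Section 2.1.12 reports grade 3 or 4 creatinine increases in 6.2% of the African trial's 1-week amphotericin B groups; 0.062 × 27 is about 1.7 patients at the planned sample size. That trial's grading criteria are not stated, so the figure is only indicative.

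**Little depends on it.** The study is descriptive and plans no test. The sample size rests on anaemia and headache, and Tables 10 and 11 do not use creatinine. This limits the importance of the point. It does not make the rows comparable, and a footnote alone would disclose the mismatch without giving the reader a comparable figure.

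**Conclusion.** The point holds as a minor reporting improvement to one of the seven Table 9 parameters. The baseline row reflects level only and the later rows reflect level or rise, so their grade 3/4 percentages are not like for like. This follows from the rule itself and needs no assumption about the data.

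With the sites' normal range, within-range grade 3 is possible for baselines of 53.0 to 76.6 µmol/L. Within-range grade 4 is possible only for baselines of 53.0 to 57.45 µmol/L, and only if the grade 4 wording is read as an increase *to* 2.0 × baseline. These limits apply to baselines inside the normal range; a baseline below 53.0 would widen both. The number of patients affected cannot be known from the documents. At n = 27, each one moves a percentage by 1 ÷ 27 = 3.7 points.

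**What to change.** Keep the combined DAIDS creatinine grade for days 7 and 14, defined as the higher of the two criteria, and add to Table 9:

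- (a) the grade by the ULN criterion alone at baseline, day 7 and day 14, named as the before/after comparison;
- (b) the grade by the ratio criterion at days 7 and 14, with the baseline cell marked not applicable.

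Below the table, give the number of combined grade 3/4 results that lie within the laboratory normal range. State in section 4.10 which criterion applies at which visit and how the grade 4 ratio wording is read.

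Cost: two extra columns and a short note. The pro forma already records creatinine at all three visits, so no new data are needed.
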